5.2 Selection of Study Population

Premenopausal female subjects (aged 18 to 51 years, inclusive) with HMB (> 80 mL blood loss per menstrual cycle) associated with uterine fibroids who meet the inclusion criteria and do not meet any of the exclusion criteria will be eligible for randomization into the study.

Each Investigator will employ their clinical judgment in conjunction with protocol specified inclusion/exclusion criteria to determine if subject meets eligibility. Questions should be directed to the AbbVie Therapeutic Area Medical Director (TA MD) listed in Section 6.1.5 if further clarification is required.

Due to the long Screening Period, eligibility should be assessed throughout the Screening Period and just prior to Randomization to ensure that subject continues to meet eligibility.

[figure not shown]
5.2.1 Inclusion Criteria

- Subject has voluntarily signed and dated the informed consent form (ICF), approved by an Institutional Review Board/Ethics Committee (IRB/EC), prior to washout (if applicable), or initiation of any screening or study-specific procedures.
- 2. Subject is a premenopausal female 18 to 51 years of age at the time of Screening.
- Subject has a diagnosis of uterine fibroids documented by a Pelvic Ultrasound (TAU, TVU) assessed by a central reader and verification that a fibroid present meets at least one of the following criteria:
 - Intramural, submucosal non-pedunculated fibroid with a diameter ≥ 2 cm (longest diameter)
 - Subserosal fibroid \geq 4 cm
 - Multiple fibroids with a total uterine volume of $\ge 200 \text{ cm}^3$ to $\le 2,500 \text{ cm}^3$
- Subject has HMB associated with uterine fibroids as evidenced by MBL > 80 mL during each of two menses in Screening as measured by the alkaline hematin method.

- 5. Subject has a Screening FSH level of < 35 mIU/mL (35 IU/L).
- 6. Subject has a negative urine and/or serum pregnancy test(s) during the Washout (if applicable) and/or Screening Periods, and has a negative urine pregnancy test just prior to first dose.
- 7. Subject must agree to use two forms of non-hormonal contraception (dual contraception) consistently during the Washout (if applicable), Screening, Treatment and Post-Treatment Periods (Subject may start hormonal contraception after completion of the Post-Treatment Month 2 Visit provided her menses has returned). Acceptable methods of dual contraception include the following combinations:
 - Condom with spermicide (foam, gel or polymer film)
 - Diaphragm with spermicide (condom may or may not be used)
 - Cervical cap with spermicide (condom may or may not be used)

Subject is not required to use dual contraception methods if:

- Sexual partner(s) is vasectomized, at least 6 months prior to Screening.
- Subject practices total abstinence from sexual intercourse, as the preferred lifestyle of the subject; periodic abstinence is not acceptable.
- Subject had a bilateral tubal occlusion (including ligation and blockage methods such as Essure[®]), at least 4 months prior to Screening.
- Subject is not sexually active with men; periodic sexual relationship(s) with men requires the use of dual non-hormonal contraception as noted above.
- 8. Subject has an adequate endometrial biopsy performed during Screening, the results of which show no clinically significant endometrial pathology.
- Subject ≥ 39 years of age at the time of randomization has a normal mammogram (BI-RADS Classification 1 to 3 or equivalent) during Screening or within 3 months prior to Screening.
- 10. Subject must agree to the Washout Intervals for hormonal therapies, including any other medication that may require washout as specified in Section 5.2.3.1.

11. Subject has not taken exclusionary hormonal therapies within the specified washout interval as specified in Section 5.2.3.1 prior to the initiation of any screening procedures and must have at least 1 menses prior to initiation of any screening procedures.

Rationale for Inclusion Criteria:

- 1 This is standard criterion in accordance with harmonized Good Clinical Practice (GCP).
- 2-5 These criteria were selected to ensure an appropriate subject population of premenopausal women with HMB associated with uterine fibroids. (prognostic and predictive)
- 6, 7 The impact of elagolix on pregnancies or breastfed infants is unknown and there is a possible risk of miscarriage due to changes in hormone levels; therefore, these criteria ensure pregnant women are not enrolled into the study and adequate precautions are taken to avoid pregnancy during study participation. (prognostic and risk)
- 8-9 These are standard criteria to ensure general good health and the safety of the subjects. (risk)
- 10, 11 To avoid bias for the evaluation of efficacy and safety by concomitant use of other medications. (predictive and risk)

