This study will utilize the alkaline hematin (AH) method for measuring MBL from screening through the first full menses in the Post-Treatment Follow-up Period. Alkaline hematin is an objective and reliable measurement of total MBL based on the quantitation of menstrual blood collected on sanitary products.

[figure not shown]
Key Criteria for Inclusion/Exclusion:

Key Inclusion Criteria:

- 1. Subject has voluntarily signed and dated the informed consent form (ICF), approved by an Institutional Review Board/Ethics Committee (IRB/EC), prior to washout (if applicable), or initiation of any screening or study-specific procedures.
- 2. Subject is a premenopausal female 18 to 51 years of age at the time of Screening.
- 3. Subject has a diagnosis of uterine fibroids documented by a Pelvic Ultrasound (TAU, TVU) assessed by a central reader and verification that a fibroid present meets at least one of the following criteria:
 - Intramural, submucosal non-pedunculated fibroid with a diameter ≥ 2 cm (longest diameter).
 - Subserosal fibroid \geq 4 cm.
 - Multiple fibroids with a total uterine volume of $\ge 200 \text{ cm}^3$ to $\le 2,500 \text{ cm}^3$.
- 4. Subject has HMB associated with uterine fibroids as evidenced by MBL > 80 mL during each of two screening menses as measured by the alkaline hematin method.
- 5. Subject has a Screening FSH level of < 35 mIU/mL (35 IU/L).
- 6. Subject has a negative urine and/or serum pregnancy test(s) during the Washout (if applicable) and/or Screening Periods, and has a negative urine pregnancy test just prior to first dose.
- Subject must agree to use two forms of non-hormonal contraception (dual contraception) consistently during the Washout (if applicable), Screening, Treatment and Post-Treatment Follow-Up Periods. (Subject may start hormonal contraception after completion of the Post-Treatment Month 2 Visit and return to first full menses). Acceptable methods of dual contraception include the following combinations:
 - Condom with spermicide (foam, gel or polymer film).
 - Diaphragm with spermicide (condom may or may not be used).
 - Cervical cap with spermicide (condom may or may not be used).

Subject is not required to use dual contraception methods if:

- Sexual partner(s) is vasectomized, at least 6 months prior to Screening.
- Subject practices total abstinence from sexual intercourse, as the preferred lifestyle of the subject; periodic abstinence is not acceptable.

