PGIC-NBUFS	Patient Global Impression of Change - Non-Bleeding Uterine Fibroid Symptoms
PID	Pelvic Inflammatory Disease
P-gp	P-glycoprotein
РК	Pharmacokinetic
POC	Proof-of-Concept
PRO	Patient Reported Outcome
PSQ	Physician Surgery Questionnaire
PTSD	Post-Traumatic Stress Disorder
QD	Once a day (quaque die)
QoL	Quality of Life
RANKL	Receptor activator of nuclear factor-KB ligand
RBC	Red Blood Cell
RR	Respiration Rate
RNA	Ribonucleic acid
SAE	Serious Adverse Event
SAP	Statistical Analysis Plan
SGOT/ASAT	Serum glutamic-oxaloacetic transaminase/aspartate aminotransferase
SIS	Saline Infusion Sonohysterography
SGPT/ALAT	Serum glutamic-pyruvic transaminase/alanine aminotransferase
SPRM	Selective Progesterone Receptor Modulator
TA MD	Therapeutic Area Medical Director
TAU	Transabdominal Ultrasound
TDD	Total Daily Dose
TBG	Thyroxine-Binding Globulin
TSH	Thyroid Stimulating Hormone
TEAEs	Treatment-emergent adverse events

[figure not shown]
TVU	Transvaginal Ultrasound
UBQ	Uterine Bleeding Questionnaire
UFS-QoL	Uterine Fibroid Symptom Quality of Life Questionnaire
WBC	White Blood Cells
WHO	World Health Organization
WPAI	Work Productivity and Activity Impairment

Pharmacokinetic and Statistical Abbreviations

ANOVA	Analysis of variance
ANCOVA	Analysis of covariance
AUC	Area under the plasma concentration-time curve
C _{max}	Maximum concentration in plasma
LOCF	Last Observation Carried Forward
NOAEL	No observed-adverse-effect levels
PD	Pharmacodynamic
РК	Pharmacokinetic
SAP	Statistical Analysis Plan
T _{max}	Time to maximum observed plasma concentration

Definition of Terms

Washout Period (if applicable)	The minimum interval of time for washout of hormonal therapy or other prohibited medications (if applicable).
Screening Period	The approximate 2.5 to 3.5 month period prior to randomization on Day 1, when screening procedures are performed to establish eligibility. Subjects may either enter the Screening Period directly, if no washout is required, or enter after completing the Washout Period (if applicable).
Day 1 (Randomization) or Treatment Period Day 1	The day a subject takes her first dose of study drug. Day 1 will occur between the first and tenth day of the onset (first day with full menstrual flow) of menses.
Monthly Visits: Treatment Period Months 1 through 6 and Post-Treatment Period Months 1 through 12	A month is defined as 28 days.

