Subjects will continue the use of dual non-hormonal contraception and receive counseling on the importance of consistent, appropriate and effective use of birth control. Subjects who prematurely discontinue from the Treatment Period will be asked to complete Premature Discontinuation procedures and enter the Post-Treatment Follow-Up Period. Premature Discontinuation Procedures will be performed as specified in Appendix C, Study Activities.

Eligible subjects who complete the 6-month Treatment Period, qualify and provide informed consent will be allowed to participate in a 6-month extension study in which all subjects will receive active treatment with either elagolix 300 mg BID alone or elagolix 300 mg BID plus E2/NETA. All activities for these subjects are outlined in the extension study protocol (Study M12-816). The Month 6 Treatment Visit in this study may be conducted over several days to allow for eligibility to be confirmed prior to participation in the extension study.

Post-Treatment Follow-Up Period

[figure not shown]
For subjects entering the 12-month Post-Treatment Follow-Up Period, visits will occur either by phone or on-site from Months 1 through 12.

During the phone visits, site personnel will discuss adverse events, concomitant medications, if applicable, obtain the results of the subject's self-administered urine pregnancy test and will remind subjects of the importance of consistent use of appropriate and effective dual non-hormonal contraception throughout the Post-Treatment Follow-Up Period. Subjects may begin taking hormonal contraceptive preparations only after completing the Post-Treatment Follow-Up Month 2 Visit and having returned sanitary products for a full menses (menses with full menstrual flow) in the Post-Treatment Follow-Up Period. If the subject's full menses has not returned by the Post-Treatment Follow-Up Month 2 Visit, an adverse event of amenorrhea should be documented.

During the on-site visits, Post-Treatment Month 1, 3, 6, 9 and 12, procedures will be performed as specified in Appendix C, Study Activities.

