5.2.3.5 Prohibited Therapy

All hormonal forms of birth control (except the emergency contraceptive pill, levonorgestrel 1.5 mg [such as Plan B[®]], or ulipristal acetate 30 mg [such as Ella[®] or EllaOne[®]]) are prohibited during the Washout, Screening; Treatment Period and until the Post-Treatment Follow-Up Month 2 Visit and return to menses. If the Subject has not returned to menses, she must continue the use of dual non-hormonal contraception.

For subjects who are prescribed/administered the emergency contraceptive pill during the study, the AbbVie TA MD must be informed.

Tranexamic acid should not be taken during the Screening, Treatment or Post-Treatment Follow-Up Period, however tranexamic acid, if necessary, can be prescribed following completion of the Post-Treatment Follow-up Month 2 visit and the subject has returned to first full menses.

Due to the extensive list of herbal remedies and supplements, please contact the AbbVie TA MD for any that may be prohibited. Generally-speaking, any supplements or herbal remedies used to treat premenstrual or gynecological problems, such as black cohosh, are excluded.

The following medications should not be taken during the Washout (if applicable), Screening, Treatment and Post-Treatment Follow-Up Period.

Table 3.Prohibited Medications

Prohibited During the Washout, Screening, Treatment and Post-Treatment Follow-Up Periods		
Hormonal/Anti-Hormonal Medications [%] , such as:	GnRH agonists leuprolide acetate (Lupron [®]), nafarelin acetate (Synarel [®]), goserlin acetate (Zoladex [®])	
	GnRH antagonists (other than elagolix)	
	Danazol (Danocrine [®])	
	Medroxyprogesterone acetate (Depo-Provera [®] , Provera [®])	
	Oral contraceptives	
	Estrogen preparations*	
	Testosterone preparations	
	Other progestins* (oral, vaginal, transdermal, implantable, IUD, or LNG-IUS, except emergency contraception)	
	HCG or HCG products	
	Glucocorticoids, oral or injectable (chronic use only)	
	Mifepristone	
	Selective Progesterone Receptor Modulators (e.g., Ulipristal acetate (except as emergency contraception, i.e., 30 mg) and Vilaprisan)	
	Tamoxifen	
	Bromocriptine (Parlodel [®])	
	Cabergoline (Dostinex [®])	
	Raloxifene (Evista [®])	
	Aromatase Inhibitors (e.g., Anastrozole [Arimidex [®]], Exemestane [Aromasin [®]])	
Non-hormonal estrogen supplements [#]	Natural Estrogen preparations (e.g., soy-containing supplements, black cohosh)	
Antifibrinolytics [%]	Tranexamic acid (Lysteda, Cyklokapron, Cyclo-f)	

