Table 3.Prohibited Medications (Continued)

[figure not shown]
Prohibited During the Washout, Screening, Treatment and Post-Treatment Follow-Up Periods		
Moderate or strong CYP3A	Strong Inducers:	
Inducers, ⁹ and Anti-epileptic medications, such as:	St. John's Wort	
	Rifampin	
	Carbamazepine	
	Phenytoin	
	Dexamethasone chronic use	
	Moderate Inducers:	
	Bosentan	
	Efavirenz	
	Etravirine	
	Modafinil	
	Nafcillin	
Bisphosphonates, RANKL inhibitors, Anabolic Bone Agents or rPTH, such as:	Fosamax [®] , Fosamax Plus D [®] , Binosto [®] , Boniva [®] , Reclast [®] , Zometa [®] , Prolia [®] , XGEVA [®] , Forteo [®] , Actonel [®] , Atelvia [®] , Miacalcin [®] , Fortical [®]	
Synthetic Prostaglandin E1 (PGE1)	Misoprostol (Cytotec [®] , Arthrotec [®])	
Analogs, such as:	Single use of PGE1 for cervical preparation prior to biopsy is allowed; chronic use is prohibited	
Oral Retinoids (topical applications are permitted), such as:	Accutane [®] (isotretinoin)	

* E2/NETA will be taken by subjects randomized to the E2/NETA dose group.

Due to the extensive list of herbal remedies and supplements, please contact the AbbVie TA MD for any that may be prohibited.

% Subjects may begin the use of hormonal contraceptives following completion of the Post-Treatment Follow-up Month 2 Visit and return to menses. Tranexamic acid, if necessary can be prescribed following completion of the Post-Treatment Follow-up Month 2 visit and the subject has returned to first full menses.

If a prohibited medication is necessary to treat an adverse event or a pre-existing condition other than uterine fibroids, the AbbVie TA MD noted in Section 6.1.5 should be consulted; however, if clinically required and to prevent an immediate hazard to the subject being treated, the AbbVie TA MD should be notified as soon as possible after the start of use. Additionally, if a subject takes a prohibited medication during the study, except as permitted per protocol (hormonal medication taken after completion of the Post-Treatment Follow-Up Month 2 Visit and return to menses), her continued

participation in the study will be evaluated by the investigator and the AbbVie TA MD. If there are any questions regarding prior or concomitant therapy, please contact your Study Monitor.

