Subjects may begin the use of hormonal contraception in place of dual non-hormonal contraception during the Post-Treatment Follow-up Period if they meet both of the following:

- Completed the Post-Treatment Follow-up Month 2 Visit
- Returned to first full menses in the Post-Treatment Follow-up Period

If subject does not return to full menses she must continue use of dual non-hormonal contraception.

The following measures will be taken to help ensure pregnancy prevention during the study.

 The informed consent form will include an attestation requiring the subject to confirm in writing her full awareness that the potential risks of study drug (elagolix) on the unborn child are unknown and therefore she must not get pregnant during the entire time of study participation, and that she agrees to consistently use dual non-hormonal contraception throughout her study participation (during the Washout Period, if applicable, Screening, Treatment and Post-Treatment Follow-Up Period.

- 2. The investigator or designated study staff will counsel the subject that the study drug is not contraceptive, that ovulation may occur even though the study drug may have altered menstrual cyclicity, and that fetal abnormalities have been observed in women who have received elagolix in clinical studies that were not deemed to be related to elagolix based on the totality of data; however, it is unknown whether these abnormalities were the result of taking elagolix.
- 3. The Sponsor will provide training materials to the sites for instructing subjects on the types of protocol-allowed contraception methods, their effectiveness and proper use.
 - The Sponsor will provide sites with a supply of materials to promote pregnancy prevention, including contraceptives (condoms and spermicides), and lubricants to provide to subjects at no charge. Subjects should only use the pregnancy prevention materials provided by the Sponsor as these products have undergone analytical testing by the analytical lab to confirm there is no or limited interference with the alkaline hematin method.
 - Subjects will be allowed to choose a contraception method of their choice from the contraceptives provided by the Sponsor and practice the allowable methods of dual contraception. The site will assess the subject's basic understanding of the proper use through discussion and demonstration of proper techniques, including proper diaphragm use.

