ác	Subject should return sanitary products within approximately 5 days after cessation of bleeding or spotting from the first menses with full menstrual flow in the Post- Treatment Follow-up Period at a Product Collection Visit or a scheduled site visit. The venous blood sample will be sent with collected products to the Alkaline Hematin laboratory. If the subject misses collecting sanitary products for her first full menses, she will be required to collect sanitary products for her next full menses.	oduct Colle llecting sam	approxima ction Visi itary prodv	ately 5 day t or a schee ucts for he	s after ces Juled site r first full	sation of b visit. The menses, sh	leeding or venous blo ve will be r	spotting f ood sampl equired to	from the fir e will be so collect sau	st menses ent with cc nitary proc	with full n ellected pro lucts for he	nenstrual fi oducts to th r next full	low in the ne Alkaline menses.	Post- e Hemat	.щ
h.	Subjects are required to continue the use of two forms of non-hormonal birth control throughout the Post-Treatment Follow-Up Period (After Month 2 in the Post-Treatment Follow-Up Period, provided the subject returned to menses, the subject may begin the use of hormonal contraception in place of non-hormonal birth control).	e use of two iject returne	o forms of	non-horm es, the sub	onal birth ject may t	control thr regin the u	oughout tl se of horm	ne Post-Tr vonal conti	eatment Fc raception in	n place of	Period (Aft non-hormc	er Month 2 mal birth c	2 in the Po control).	st-Treat	ment
	Post-Treatment UBQ will only be completed if Subject has not returned sanitary products for her first full menses in the Post-Treatment Period at the time of the Phone or Site visit. Once a Subject returns sanitary products from her first full menses in the Post-Treatment Eollow-up Period, the Post-Treatment UBQ no longer needs to be completed.	ompleted if y products	Subject h from her 1	as not retu first full me	rned sanit enses in th	ary produc te Post-Tre	ts for her atment Fo	first full m llow-up Po	nenses in the I eriod, the I	ie Post-Tre Post-Treati	atment Per nent UBQ	riod at the no longer	time of the needs to b	e compl	or Si leted.

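### Protocol 5.1 alone makes hormonal contraception in follow-up depend on returned products, and SAP 11.3.5.4 can report a later menses as the first when the first was not collected

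*Protocol*

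**What the plan says.** **Hormonal contraception in follow-up.** Every section requires the follow-up Month 2 visit to be completed. They differ on the second condition.

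- Protocol 5.1 (Post-Treatment Follow-Up Period) requires "having returned sanitary products for a full menses (menses with full menstrual flow) in the Post-Treatment Follow-Up Period".
- The synopsis, criterion 7, reads "Subject may start hormonal contraception after completion of the Post-Treatment Month 2 Visit and return to first full menses". Section 5.2.4 lists the same two conditions and adds "If subject does not return to full menses she must continue use of dual non-hormonal contraception".
- Section 5.2.1, criterion 7, reads "Subject may start hormonal contraception after completion of the Post-Treatment Month 2 Visit provided her menses has returned". Section 5.2.3.5 prohibits hormonal birth control "until the Post-Treatment Follow-Up Month 2 Visit and return to menses". The Table 3 footnote reads "Subjects may begin the use of hormonal contraceptives following completion of the Post-Treatment Follow-up Month 2 Visit and return to menses", and note h to the follow-up schedule in Appendix C reads "provided the subject returned to menses, the subject may begin the use of hormonal contraception".

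**Amenorrhea adverse event.** Section 5.1 triggers it when full menses has not come back by the Month 2 visit. Section 6.1.1.1 and the matching note in Appendix C speak of menses, without *full*.

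**Collection and analysis.** Under 5.1, a woman who misses collecting her first full menses collects the next one. Until products from a full menses are in, staff ask her the post-treatment Uterine Bleeding Questionnaire (UBQ, Appendix H) at each contact. SAP 11.3.5.4 measures time from last dose to the first day of the first post-treatment menses, using observed alkaline hematin (AH) data. It counts as menses any episode with at least one day of bleeding or spotting. Protocol 5.3.5 lists this time as a safety variable.

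**The concern.** Two separate problems meet at the same event, a first full menses that was not collected.

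The first is conduct. One section refuses such a woman hormonal contraception and the others allow it. Section 5.2.3.5 sends a woman who takes a prohibited drug to a review of her continued participation, unless the protocol permits the use. It states that permission without any collection condition. Deviations are reported under Section 7.0 and summarised by treatment group under SAP 6.0. The same act can therefore count as compliant or as a deviation, depending on the section a site follows.

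The second is measurement. For a drug that suppresses ovarian function, time to first menses after stopping describes recovery. SAP 11.3.5.4 has no rule for a bleed that happened but was not collected, so a later menses can stand in for the first without any mark in the table. If that later menses began on hormonal contraception or tranexamic acid, its volume may also be lowered. Protocol 3.1 names oral contraceptives and tranexamic acid as short-term treatments for heavy bleeding.

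**Working it through.** **1. The contraception wordings side by side**

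| Place in Protocol | Second condition | Product return needed? |
|---|---|---|
| 5.1 | products from a full menses returned | yes |
| Synopsis; 5.2.4 | first full menses has occurred | no |
| 5.2.1; 5.2.3.5; Table 3 footnote; Appendix C note h | menses has occurred | no |

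The last two rows are probably one rule. The definition of Day 1 in Section 1.3 places it "between the first and tenth day of the onset (first day with full menstrual flow) of menses", so the protocol's ordinary use of menses onset is full flow. No such reading absorbs the 5.1 condition. Consider three women who have completed the Month 2 visit:

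- Full menses occurred and was collected: permitted everywhere.
- No menses yet: barred everywhere.
- First full menses occurred but was not collected: barred by 5.1, permitted by every other section.

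The tranexamic acid condition is the same in the synopsis, 5.2.3.5 and Table 3, and is not part of the conflict.

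**2. When the SAP date is late**

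Three conditions must all hold: (i) the first full menses was not collected; (ii) no earlier post-treatment bleeding or spotting was collected; (iii) a later menses was collected. If (ii) fails, the SAP dates her from the earlier spotting, because one spotting day counts as menses. If (iii) fails, she has no observed date.

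**3. How late, per affected woman**

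The bounded categories in SAP 11.3.5.4 are 28 days wide (Study End Days 1–28 up to 141–168). For a true start on day s of a category (s = 1 to 28) and a delay of d days:

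categories moved = floor((s − 1 + d) / 28)

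Post-treatment cycle length is not given. I assume 24 to 38 days. The 38 is borrowed from exclusion criterion 1 (5.2.2), which concerns cycles before screening; the 24 has no source in the documents. The percentages take start days as evenly spread within a category.

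| d | 0 categories | 1 category | 2 categories |
|---|---|---|---|
| 24 | s = 1–4: 4/28 = 14% | s = 5–28: 24/28 = 86% | none |
| 28 | none | 28/28 = 100% | none |
| 38 | none | s = 1–18: 18/28 = 64% | s = 19–28: 10/28 = 36% |

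**4. Effect on the table, illustration only**

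Let m be the share of women meeting all three conditions. The documents do not give m. As a starting distribution take Cohort 1 of the Phase 2b fibroid study (Protocol 3.2.2). Among women amenorrheic on entering follow-up, 52% returned to menses at Month 1 and a further 42% at Month 2, which is 94% together. With a delay of exactly one category, the first category becomes 52 × (1 − m), the share by Day 56 becomes 94 − 42m, and the mean overstatement is m × cycle length.

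| m (assumed) | Days 1–28 | by Day 56 | mean overstatement, 24 to 38 day cycles |
|---|---|---|---|
| 5% | 49.4% | 91.9% | 1.2 to 1.9 days |
| 10% | 46.8% | 89.8% | 2.4 to 3.8 days |
| 20% | 41.6% | 85.6% | 4.8 to 7.6 days |

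**The case against.** The best defence is that most of this is loose wording. On the amenorrhea event it largely succeeds. A reader might infer that sites work to two different triggers. However, Protocol 5.3.1.1 says that collecting the first full-flow menses in follow-up serves to assess return to menses, and its text on phone contacts tells staff to assess return to full menses. Full flow is very likely the intended test throughout, so this part is an alignment of words and no more. For the same reason the documents do not support reading three distinct contraception rules into the text.

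A reader might also infer that every woman with a missed first collection is dated late. Step 2 of the working shows otherwise.

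Nor is the SAP at odds with itself because it uses the UBQ during treatment. SAP 7.6.1.1 uses those answers only to assign a volume of zero, never to date or measure an uncollected bleed. The post-treatment form has no onset date and does not separate spotting from full menses, so AH data are the only dated source considered here.

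Finally, the 5.1 condition has a merit: it is the only wording that secures a collected full menses before hormones start. Removing it has a price, stated under the fix. What stands is the product-return conflict, and the absence of any rule in SAP 11.3.5.4 for an uncollected first menses.

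**Conclusion.** The point holds and is minor. Section 5.1 conflicts with the rest of the protocol for one definable woman, whose first full menses occurred but was not collected. The SAP reports a later menses as the first when the three conditions in the working are met. The error per affected woman is about one cycle, usually one 28-day category, on an assumed cycle of 24 to 38 days. The number of women affected cannot be derived from the documents, and the table-level figures rest on assumed shares.

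A reader might infer that efficacy conclusions are at risk. They are not. SAP 11.1 plans no hypothesis tests for efficacy in follow-up unless otherwise specified, and SAP 12.1 rules out safety testing there. The primary and ranked secondary endpoints use treatment-period data only. What is exposed is a descriptive safety summary, the matching volume summary, deviation counts and, weakly, amenorrhea reporting.

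**What to change.** 1. **One contraception rule.** Use the 5.2.4 rule throughout: Month 2 visit completed and first full menses returned. Amend 5.1, 5.2.1, 5.2.3.5, the Table 3 footnote and Appendix C note h to match. Leave the tranexamic acid condition as it is. The cost is that some women's only collected menses may then fall on hormonal contraception. Aligning everything to 5.1 would also end the conflict and would protect collection, but a woman who missed one collection would wait for another full menses before she could start.

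2. **One amenorrhea wording.** Use no full menses by the Month 2 visit in 5.1, 6.1.1.1 and the Appendix C note.

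3. **Two sentences in SAP 11.3.5.4.** In the time table, flag women whose post-treatment UBQ reports an earlier uncollected bleed, or who started hormonal contraception before any observed menses. In the volume summary, leave out or show separately any menses that begins after the start of hormonal contraception or tranexamic acid.

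No new data are needed: the UBQ answers are already collected, and so are medication start and end dates (Protocol 5.2.3.2). The volume denominator shrinks by an unknown amount. Because of the UBQ's limits, it supports a flag but not a corrected date.
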